For the surgeon infiltration, the patient will be brought directly to the operating room where intraoperative anesthetic with an opioid-sparing MAC technique will be provided as described below. Just prior to the skin incision, 0.25% bupivacaine will be used to infiltrate the dermis and subcutaneous space in the proposed incision. Throughout the procedure, additional incisional bupivacaine infiltration into the surrounding tissues will be performed as needed for local anesthesia. A total of up to 30 mL of 0.25% bupivacaine will be divided equally for the two sides of the incision. An additional 5 mL of 0.25% bupivacaine will be infiltrated into the pectoralis major muscle at the deep margin of resection. Accidental intravascular injection is minimized by continuous needle movement and frequent aspiration.

The following vital signs will be monitored throughout the procedure: Heart rate, blood pressure, oxygen saturation, and respirations, and patient's state of consciousness. We will monitor the patient until they are brought to the operating room for surgery.

All patients will receive multimodal analgesia in the preoperative area. They will receive 975 mg of oral acetaminophen and 300 mg of gabapentin orally prior to surgery. The intraoperative anesthetic will be an opioid-sparing MAC anesthetic. If patients are unable to tolerate procedure under MAC they would be converted to a general anesthetic with an laryngeal mask airway (LMA). For those patients receiving a lumpectomy with axillary dissection, they will receive a general anesthetic with LMA. Patients will receive IV midazolam 0-2 mg followed by 40-100mg of IV lidocaine, and followed by a propofol infusion and a 0.25 mg/kg bolus of ketamine followed by 0.25 mg/kg /hour infusion of ketamine. Opioids will be avoided unless HR or BP increases by 20 % above baseline. Then only short acting opioids (fentanyl) will be given.

In the recovery room if the patient experiences pain greater than 5/10 they will receive either IV or oral pain medications. If pain score is less than 5 patients will get non opioid medications unless the patient desires an opioid medication.

When the operation is complete the patient will either be brought to the PACU or Phase II. Each day a member of the research team will contact and evaluate the patient for signs of complications and ask the patient their minimum and maximum pain score

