(scores will be evaluated at 1 hr, 2 hr, 6hrs, 24hrs, 48hrs, 72hrs). They will record daily opioid use, any modality related complications, how many phone calls were made regarding pain control and modality related complications. At time period 72 hours a Quality of recovery survey (see appendix) and OBAS (see appendix) survey will be presented to patient. Patients will be offered phone calls for contact, but patients may opt to be contacted via text message if they do not wish to have phones calls. We will provide patients with an additional consent for text messaging if they wish to use this method.

At 3 months, 6 months, and 12 months patients will be called to answer a survey with regards to chronic pain.

Patients will be instructed to take acetaminophen 1000 mg every 8 hours while at home for 3 days. They will be given a prescription of opioid pain medications either oxycodone or hydromorphone and will be instructed to take as needed for pain.

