### **Assessments:**

Post-operatively patients will be evaluated 1 and 2 hr post-operatively by the PACU nurse and 6 hrs post-operatively by a medical student or research coordinator. This person will not be aware of the patient's mode of analgesia. The medical student or research coordinator will evaluate at, 24, 48, and 72 hours post injection +/- 5 hours. If sent home they will be contacted via preferred contact method at, 24, 48, and 72 hours post-operatively. Patients will be asked to rate their pain on scale of 0-10. The amount of opioids used by the patient will be recorded as will any other adjuvant pain medication used. Any modality related complications will be recorded. The patients will be asked at 72 hours post-injection to fill out a quality of recovery and OBAS survey. All complications will be recorded from time of consent to last follow up date. Patients will be called at 3, 6, and 12 months post operatively to fill out a chronic pain survey.

All data will be recorded in a locked encrypted database. Data collection will continue until Postoperative day ( POD ) #3. Should patients be re-admitted to the hospital in the next two weeks (Up to POD #19) for pain a notation will be made in study records. Additional contacts by the research assistant or medical student will continue up until the 3, 6, and 12 month postoperative times.

An analysis of the total cost of analgesics (including patient costs for opioid prescriptions) will be tabulated at the conclusion of the study to determine the most cost effective treatment option as this will be added into the cost of hospitalization including the number of days each patient spent in the hospital.

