### **Stopping Criteria:**

This study will be stopped if 5% of the subjects experience local toxicity. If  $\geq 10\%$  of the subjects develop an infection at the injection site, the protocol will be discontinued. Additionally, if any patient experiences a serious adverse event as a result of the study medications as determined by the principle investigator, they will be discontinued from the study.

Local anesthetic toxicity is defined as patients who experience local anesthetic toxicity symptoms such as new onset of tinnitus, metallic taste in mouth, numbness around lips, seizures, heart block or new arrhythmia after injection of local anesthetic for up to monitoring period of 5 days.

**Notification:** When a study participant, voluntarily or involuntarily, is eliminated from the study protocol, the Principal Investigator and Associate Investigators will be notified.

**Adverse reactions:** Adverse or unexpected occurrences resulting from the treatment utilized in the protocol will be reported to the Principal Investigator and the Associate Investigators. These individuals will discuss these reactions or untoward events and implement changes in the protocol accordingly. Investigators will meet regularly to discuss problems encountered with the study protocol.

**Modifications to protocol:** Alterations that may become necessary in the protocol during the study period will be made by agreement of the investigators. Patients will be notified of any relevant protocol changes.

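### The toxicity stopping rule counts mild symptoms for up to 5 days, but no contact is explicitly scheduled after about 72 hours, so on days 4 and 5 the count relies on volunteered or charted reports

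*Combined protocol and SAP*

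**What the plan says.** **Stopping Criteria.** The study stops if 5% of subjects experience local toxicity. Toxicity is defined as "new onset of tinnitus, metallic taste in mouth, numbness around lips, seizures, heart block or new arrhythmia after injection of local anesthetic", and it counts "for up to monitoring period of 5 days".

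**Treatment technique.** After surgery, "Each day a member of the research team will contact and evaluate the patient for signs of complications" and asks for minimum and maximum pain. The parenthesis that follows says "scores will be evaluated at 1 hr, 2 hr, 6hrs, 24hrs, 48hrs, 72hrs". Patients can choose the medium: "patients may opt to be contacted via text message if they do not wish to have phones calls". Later, "At 3 months, 6 months, and 12 months patients will be called to answer a survey with regards to chronic pain".

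**Assessments.** The student or coordinator evaluates at 24, 48 and 72 hours after injection, within 5 hours either way. For discharged patients, "If sent home they will be contacted via preferred contact method at, 24, 48, and 72 hours post-operatively". The section then says "Data collection will continue until Postoperative day ( POD ) #3". It also states that complications are recorded from consent to last follow-up, that readmission for pain is noted for a period after surgery, and that further contacts continue up to the 3-, 6- and 12-month times.

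**Data collection.** The items to be recorded at 72 hours include readmission over the following month and any complications. No contact at one month is scheduled.

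**The concern.** A stopping rule depends on how completely its numerator is collected. This plan sets its own 5-day window and includes symptoms that only the patient can report. Tinnitus, a metallic taste or numb lips at home will seldom bring a patient back to hospital and would not normally meet the serious adverse event criteria, so the route to the safety board is unlikely to supply them. If nobody asks after about 72 hours, the count can miss cases that the definition includes.

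What is at stake is the completeness of one safety count. The primary outcome, total opioid use, and its analysis are not involved.

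**Working it through.** **Inputs**
- Window: 5 days from injection (Stopping Criteria).
- Last early contact with a stated time: 72 hours (Treatment technique; Assessments), with a tolerance of 5 hours either way (Assessments).
- Next contact with a stated time: the 3-month chronic pain survey (both sections).
- Threshold: 5% of subjects (Stopping Criteria); 112 to be enrolled (Statistical Considerations).

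**Uncovered time.** Gap = window − time of last contact, with the window at 5 × 24 = 120 h.

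| Last contact after injection | Gap | Share of window |
|---|---|---|
| 67 h (72 − 5) | 120 − 67 = 53 h | 53/120 = 44% |
| 72 h | 120 − 72 = 48 h | 48/120 = 40% |
| 77 h (72 + 5) | 120 − 77 = 43 h | 43/120 = 36% |

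**Clock.** The tolerance sentence counts from injection, whereas the sentence on discharged patients counts from surgery and repeats no tolerance. The time from injection to end of surgery is not given. If it were 1 to 4 h (an assumption), a contact exactly 72 h after surgery would leave 120 − 73 = 47 h to 120 − 76 = 44 h, inside the range above. If the tolerance also applied, the latest contact would be at 77 + 4 = 81 h and the gap 39 h (39/120 = 32.5%). The gap remains more than a day and a half in every case.

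**Does any other sentence fill the gap?**
- The daily contact for complications has no stated end. The 72-hour list that follows it governs pain scores, so it does not strictly end the complication checks. The data-collection sentence points to day 3, but no text says that the checks run to day 5.
- Recording complications to last follow-up states an intention. It sets no day 4 or 5 contact through which a mild symptom would become known.
- The further contacts up to the 3-, 6- and 12-month times have no dates before 3 months and no toxicity content.
- The one-month item on readmission and complications sits in the 72-hour list and has no contact of its own.
- Physician reporting (Risks) needs the event to reach a physician, and no visit is set for days 4 and 5.

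**Threshold.** 0.05 × 112 = 5.6, so six cases trigger the rule at full enrolment. The section does not say when the rule is applied during accrual. The documents give no event rate, so the number of missed cases cannot be estimated.

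**The case against.** The strongest reply is that the gap is inferred. The daily complication check is open-ended, the 72-hour list concerns pain scores, and the Stopping Criteria section itself names a 5-day monitoring period. Read together, daily checks to day 5 are a tenable reading. The further contacts and the one-month complication item also suggest that capture beyond day 3 was intended. This stands in part: the documents do not show that monitoring stops at 72 hours, and a reader who infers that goes too far. What they do show is that no day 4 or 5 toxicity check is written down, and that the sentence ending data collection at day 3 points the other way. Staff following the text could reasonably stop at 72 hours.

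A second reply is that an outer limit for counting events does not promise active questioning on every day. That is fair, and passive capture is adequate for seizure, heart block or arrhythmia. It is weaker for symptoms that only the patient can notice.

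A third reply is that nothing suggests mild symptoms first arise so late. The only durations given (Background and Significance) are for analgesia: up to 24 hours for bupivacaine and up to 72 hours for the liposomal form. These are not a toxicity time course and settle nothing either way. They do mean that the 36% to 44% must not be read as a share of cases missed, and that no changed stopping decision has been shown.

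**Conclusion.** The point holds as a minor mismatch between the safety window and the written contact schedule. About 43 to 53 of 120 hours have no explicitly scheduled contact, taking the documented 5-hour tolerance as measured from injection. Days 1 to 3 are covered. The exposure is confined to mild symptoms that first arise on days 4 and 5 in discharged patients, and these count only if volunteered or charted.

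The effect is probably small. That judgement rests on severe events usually reaching the chart, and it cannot be firmed up because the documents give neither event timing nor an event rate. A reader might infer that the stopping rule is unworkable or that some 40% of toxicity goes unseen; the documents support neither.

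**What to change.** Keep the 5-day window. State in Treatment technique and in Assessments that complication checks run to day 5 after injection. Add one brief scripted text or call at the end of day 5 that asks about each symptom in the Stopping Criteria definition, using the phone and text contact already offered.

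The cost is at most 112 short extra contacts, a small burden on patients and staff, and a sentence or so of protocol wording. The sample size, primary outcome and analysis do not change. A question on injection-site infection, which has its own stopping threshold, could go into the same contact, but it is optional and not part of this defect.

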### **Definition of Adverse Event (AE):**

Any untoward medical occurrence associated with the use of a drug in humans, whether or not considered drug related. An AE (also referred to as an adverse experience) can be any unfavorable and unintended sign ( e.g., abnormal laboratory finding), symptom, or disease temporally associated with the use of a drug, without any judgement about causality. An AE can arise from any use of the drug (e.g., off-label use in combination with another drug) and from any route of administration, formulation, or dose, including an overdose.

An AE can be any unfavorable and unintended change in a body structure or body function. Adverse events include any clinically significant deterioration of a subject's medical status. The AE may involve any organ or system and can be represented by the new onset or the deterioration of a disease, a syndrome, a symptom, a physical sign, as well as by findings and results of instrumental examinations and laboratory tests. Any medically relevant and untoward change after the subject signs the ICF, including frequency or pattern changes for a fluctuating condition (e.g. migraine) is considered an AE.

An AE that occurs after the ICF has been signed and before the start of the study drug administration is identified as a pretreatment AE (PTAE). An AE that occurs after the administration of a study treatment is considered a treatment emergent AE (TEAE).

**Definition of Adverse Reaction:**

Any AE caused by a drug. Adverse reactions are a subset of all suspected adverse reactions for which there is reason to conclude that the drug caused the event.

**Definition of Suspected Adverse Reaction:**

Any AE for which there is a reasonable possibility that the drug caused the AE. For the purposes of IND safety reporting, ‘reasonable possibility’ means there is evidence to suggest a causal relationship between the drug and the AE. A suspected adverse reaction implies a lesser degree of certainty about causality than adverse reaction, which means any AE caused by a drug. Suspected adverse reactions are a subset of all AEs for which there is a reasonable possibility that the drug caused the event.

**Severity of Adverse Events:****Relationship of Adverse Events to Study Drug:**

The Investigator will assess the relationship of the AE to study drug after careful medical consideration, on a case-by-case basis. General guidelines are provided as follows:

Not Related: A causal relationship between the study drug and the AE can be easily ruled out (e.g., based on the temporal sequence, absence of a reasonable pathophysiological mechanism, or direct evidence of actual cause).

Related: There is a reason to conclude that the drug caused the event (i.e., there is a reasonable possibility based on evidence to suggest that the drug caused the event).

**Definition of a Serious Adverse Event:**

Definition of a serious adverse event (SAE). An AE is considered “serious” if, in the view of either the Investigator or Sponsor, it results in any of the following outcomes:

- Death
- A life-threatening adverse event
- Inpatient hospitalization or prolongation of existing hospitalization
- A persistent or significant incapacity
- Congenital anomaly/birth defect
- Medically significant

Any Serious Adverse Event will be reported to the local IRB within 5 days

**Use of information and publications arising from the study:** Information gained from the interpretation of the data collected in this study will be used for the preparation of a scientific publication, and a presentation to a peer review journal and scientific meetings.

Prior to submission of information for publication or presentation, a written assessment of the data will be presented to the Primary Investigators at UMMC.

